# 13.9 Unscheduled visit

If a subject returns for a potential study related cardiovascular or neurological visit outside of the protocol-defined visit schedule provided in Table 13.8A, the visit will be considered "unscheduled" (UNS). An Investigator may request an unscheduled visit in the presence of a new or worsening cardiovascular condition or neurological deficit. If the unscheduled visit is for a repeat ablation procedure, the protocol follow-up schedule is based on the index ablation procedure. For all unscheduled visits, an unscheduled visit eCRF must be completed and the subject must also return for their next scheduled study visit.

## 13.10 Heart Rhythm Monitoring

ECG, Transtelephonic monitors (TTM) and Holter Monitors will be used to monitor the subjects' heart rhythm post-treatment.

Transtelephonic Monitors (TTM):

Transtelephonic monitors (TTM) will be provided to each subject no later than at the 3month follow-up visit for scheduled transmissions of heart rhythm status. Subjects will be instructed to transmit all emergent symptomatic cardiac events and follow a detailed schedule if the subject remains asymptomatic post ablation during the Evaluation Period (Day 91-365).

The TTM transmission schedule:

- Subjects will complete a test transmission upon receipt of the TTM device to demonstrate a working understanding of the device.
- Transmission will be performed once every week during the Evaluation Period, starting no later than the month 3 visit through the end of month 5 of the follow-up period. Starting from month 6, subjects will record and transmit once every month until the end of the 12- month follow-up period.
- All symptomatic cardiac episodes should be recorded and transmitted soon after the event occurs during the Evaluation Period (Day 91-365).

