	subject with freedom from documented left atrial arrhythmia (atrial fibrillation (AF), atrial tachycardia (AT) or atrial flutter (AFL)) episodes during the effectiveness evaluation period (Day 91-365)
Secondary Objectives	
 
The major secondary objectives of this study are:
 
Safety: 
 
to evaluate the incidence of serious adverse events during and after procedure up to 3 months following procedure.
 
 
 
Acute Effectiveness: 
 
Acute Procedural Success as defined by:
 
The % of subjects with electrical isolation of PVs (entrance block) at the end of the procedure, and
 
The % of subjects with electrical isolation of PVs (entrance block) using QMODE+ as only ablation strategy
 
The % of subjects with electrical isolation of PVs (entrance block) at all power settings combined
 
The % of subjects with electrical isolation of PVs (entrance block) at all power settings combined
 
The % of subjects with electrical isolation of PVs (entrance block) after waiting period and adenosine challenge
 
 
 

Exploratory Objectives	N/A
Primary Endpoints & Follow-up Intervals	
 
Acute Safety:
 
Incidence of early onset primary adverse events (PAE) related to the device or procedure. Occurrence of Primary AEs within 7 days of an
 

	ablation procedure. (refer to Appendix A for a comprehensive	
	definition list of primary adverse events)	
	12-Month Chronic Effectiveness:	
	• Freedom from documented (Symptomatic and asymptomatic) atrial arrhythmia (atrial fibrillation (AF), atrial tachycardia (AT) or atrial flutter (AFL)) episodes during the effectiveness evaluation period (Day 91-365)	
	Effectiveness Monitoring:	
	Effectiveness monitoring will include event Monitoring (TTM). Each subject will be provided an event monitor (Transtelephonic monitor, TTM) no later than at the 3-month visit, episodes $\geq 30$ secs on TTM or continuously recorded on the standard 12-leads ECG will be considered recurrence. Subjects will be expected to transmit asymptomatic recordings once every week starting no later than the month 3 visit until the month 6 visit. Starting from month 6, subjects will record and transmit once every month until the end of the 12-month follow-up period. All symptomatic cardiac episodes should be recorded and transmitted soon after the event occurs during the Evaluation Period (Day 91-365).	
	Secondary Safety Endpoints:	

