	The Final analyses for primary safety and effectiveness endpoints will apply Bayesian methods and use a beta-binomial model (assuming early success is not achieved for the primary effectiveness endpoint).
Statistical Analysis	For the Variable flow study:
	Primary Safety Endpoint
	Sample Size and Power Calculations
	
 
Based on a performance goal of 14%, an anticipated rate of 7% for the primary safety endpoint, with borrowing up to 91 subjects from the main study, the sample size of 92 subjects, will provide close to 80% power for testing the primary safety endpoint controlling one- sided alpha of 2.5%, assuming a 5% attrition rate in the variable flow study.
 

	Primary Effectiveness Endpoint
	Sample Size and Power Calculations
	• Based on a performance goal of 50%, and anticipated freedom from AF/AT/AFL recurrence rate of 65%, with borrowing up to 91 subjects from the main study, the sample size of 92 subjects will be required to obtain at least 80% power to achieve success for primary effectiveness endpoint controlling one-sided alpha of 2.5%, assuming a 12% attrition rate in the variable flow study.
	The analyses for primary safety and effectiveness endpoints will apply Bayesian methods and use a beta-binomial with data borrowing from the Main study using a propensity score-integrated power prior approach.
Interim Analysis	One early success claim interim analysis will be executed for main study
Determination if DMC/CEC required	CEC will be convened to adjudicate the primary safety endpoint. Data Monitoring Committee (DMC) will be responsible for reviewing the study results. The same committees will be responsible for both studies.

	
 
Subjects will be evaluated prior to the procedure, prior to discharge, and post procedure at 7 days (7-10 days), 1 month (23-37 days), 3 months (76-104 days), 6 months (150-210 days), and 12 months (335-395 days) unless otherwise specified in the protocol.
 
Baseline 
 
Demographics
 
Medical History
 
AAD Medication History
 
Arrhythmia History
 
Quality of Life Assessment
 
Quality of Life – Atrial Fibrillation Effect on Quality of life (AFEQT)
 
Device Interrogation (if applicable)
 
TTE or TEE evaluation
 
 
 
Ablation Procedure 
 
Ablation procedure strategy outside of the pulmonary vein ostia will utilize QMODE +/ QMODE and Investigator's Standard of Care
 
 
 

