### **Both Studies**

Effectiveness and safety endpoints have been defined and will be compared to predetermined performance goals. Subjects who sign informed consent are considered enrolled in the study. Enrolled subjects who satisfy all eligibility criteria will then undergo the ablation procedure with the QDOT MICROTM catheter.

After the study ablation procedure, subjects will enter a 3-Month blanking period (Day 0-90).

After the Blanking Period, subjects will enter the Evaluation Period (Days 91-365). Subjects having AF recurrence and/or receiving therapeutic interventions during the evaluation period will be considered effectiveness failures (refer to Section 8.2.2 for all effectiveness failure modes).

All subjects will undergo follow up visits at defined intervals (refer to Table 13.8A Schedule of Treatments and Evaluations). Subjects complete the IDE study after the 12-month follow up visit.

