  - **Electrocardiogram** (12-Lead ECG). Data from 12-lead ECG recordings will be collected at the 3M and 12M follow-up visit (standard of care are acceptable). ECG data will be collected at baseline, pre-discharge, and unscheduled visits if completed as standard of care and at 1M and 6M if a clinical visit occurs and ECG is completed as standard of care.
  - **Transtelephonic Monitoring (TTM):** Subjects will be asked to transmit any symptom-triggered episode that occurs from the time they receive the TTM device through the 12M follow-up visit. See Section 13.10 for the TTM transmission schedule. A core lab will be used to evaluate and assess the TTM tracings.
  - **24 Hour Holter:** Holter monitor will be used at the 12M follow-up visit to monitor the subjects' heart rhythm for 24 hours continuously. A core lab will be utilized to evaluate and assess the 24-hour Holter recordings.
  - **Cardiac Multi Slice CT/MRA Image:** CT/MRA will be completed at the 3M follow-up visit for subjects in the Main study CT/MRA subset. In addition, any subjects who have symptoms suggestive of PV stenosis should undergo CT/MRA imaging.
  - Adverse Events: AEs must be collected from the time the subject signs the informed consent onwards.
  - AFL/AT/AF recurrence
  - **Repeat Ablation:** Any ablation procedure performed after the index procedure will be recorded at 3M, 6M, and 12M follow-up as well as at any unscheduled visits.

- Health Economic Data for hospitalizations, ER visits and outpatient visits, if any
  - At each follow-up visit, health economic data to be collected may include, but is not limited to: hospitalization charge (UB04), repeat ablation procedure and/or procedures resulting from the ablation procedure, outpatient visits, and ER visits
- End of Study Report (12-Month)

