# **30.3.1** Effectiveness Profiles

In order to simulate the effectiveness outcome for a virtual subject, we need to simulate whether the subject has a failure and when that failure occurs. As previously discussed in section 29.2.3, a piecewise exponential time-to-failure model is assumed and calibrated to

	Biosense Webster, Inc	
Version 5.0 – Feb 3, 2021	CONFIDENTIAL	Page 129 of 135

have a particular failure rate  $(1 - p_E)$  at the end of follow-up. The profiles are constructed by taking advantage of the relationship:

$$p_E = \exp(-[2h_1 + (8-2)h_2 + (39-8)h_3]),$$

where  $p_E$  is the failure-free rate at 12-months. Previous study of catheter is assumed to estimate the hazard rates for the three pieces. From ThermoCool SSED, the reported hazard rates have the following pattern:

$$h_1 = (38.06)h_3; h_2 = (1.71)h_3; h_3 = (1)h_3.$$

To simulate data, we use the above multiplicative factors from ThermoCool and then find a value for  $h_3$ , such that when multiplied by each of the assumed rates for the three-time intervals, the failure-free rate at 12 months (39 weeks following 13weeks blanking period) matches the desired scenarios. Table 1 shows the derived hazard rates that were used to simulate data for a range of assumed failure-free rates.

	Hazard Rate (h)					
Failure-free Rate	$h_1$	$h_2$	$h_3$			
0.50	0.2248	0.0101	0.0059			
0.55	0.1938	0.0087	0.0051			
0.60	0.1656	0.0074	0.0044			
0.65	0.1397	0.0063	0.0037			
0.70	0.1157	0.0052	0.0030			
0.99	0.0032	0.0001	0.0001			

 Table 1: Parameters to generate failure times

In order to compute the predictive probability of success for the effectiveness endpoint, 2500 imputations were performed for each subject with missing outcome in the simulations

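### The event monitor may be issued up to 13 days after the evaluation period opens, at the point where the sponsor's model puts its highest failure hazard

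*Protocol*

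**What the plan says.** - **Device issue.** Protocol 13.10 has the TTM "will be provided to each subject no later than at the 3month follow-up visit for scheduled transmissions of heart rhythm status". The synopsis (Protocol 4.0, Effectiveness Monitoring) gives the same outer limit, and Table 13.8A first marks TTM at the 3-month visit.
- **Visit window.** Protocol 13.7 and Table 13.8A allow the 3-month visit on Days 76-104.
- **Evaluation period.** It runs from Day 91 to Day 365 (Protocol 8.1, 8.2.2). Section 13.10 asks for weekly transmission during this period, yet lets it begin as late as the 3-month visit.
- **Symptom-triggered recordings.** Protocol 13.7: "Subjects will be asked to transmit any symptom-triggered episode that occurs from the time they receive the TTM device". They too begin only when the device is in hand.
- **End of weekly transmission.** The synopsis has it "starting no later than the month 3 visit until the month 6 visit"; section 13.10 has it run "through the end of month 5 of the follow-up period".
- **Failure model.** Protocol 30.3.1 uses the pattern "h_1 = (38.06)h_3; h_2 = (1.71)h_3; h_3 = (1)h_3" for weeks 0-2, 2-8 and 8-39 after blanking.

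**The concern.** No section requires the TTM to be issued, or a first transmission made, by Day 91. A subject seen late in the visit window therefore starts the evaluation period with both TTM routes closed, scheduled and symptom-triggered. The sponsor's model gives these first two weeks a hazard about 38 times the late one.

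The direction of any error is fixed. Each study is a single arm tested against a 50% goal, so no concurrent control shares the loss. Under Protocol 18.9.7, a subject with full follow-up and no recorded failure stays in the final effectiveness analysis as a success. The population has self-terminating AF, so an early episode need not be seen again. Ascertainment would then depend partly on when the 3-month visit was booked. Main-study outcomes are also borrowed into the Variable Flow analysis (SAP 7.4), so a loss in the first study can carry into the second.

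**Working it through.** **1. Reproduce the plan's hazards (Appendix D, Table 1).** With success rate p, h3 = -ln(p) / (2 x 38.06 + 6 x 1.71 + 31) = -ln(p) / 117.38. At p = 0.65, h3 = 0.4308 / 117.38 = 0.0037, h1 = 38.06 x h3 = 0.1397 and h2 = 1.71 x h3 = 0.0063 per week. All three match Table 1.

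**2. Share of failures in the first two weeks.**
- Cumulative hazard: 76.12 / 117.38 = 65%.
- Subjects failing at p = 0.65: 1 - exp(-2 x 0.1397) = 24.4% of all subjects.
- Share of failures: 24.4 / 35 = 70%. The same calculation gives 72% at p = 0.50 and 69% at p = 0.70.

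**3. Longest gap.** Issue on Day 104 leaves Days 91-103 uncovered: 13 days, or up to two weekly transmissions. In 13 days the model has 1 - exp(-(13/7) x 0.1397) = 22.8% of subjects failing at p = 0.65, which is 65% of failures. This is the permitted extreme for one subject, not the average.

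**4. Average gap.** The documents do not give the distribution of visit dates. Assume that visits are uniform over the 29 days from 76 to 104 and that every device is issued at the visit. A visit on Day v after Day 91 leaves g = v - 91 uncovered days, so 13 of the 29 possible days leave a gap.
- Mean gap: (1 + 2 + ... + 13) / 29 = 91 / 29 = 3.1 days.
- Subjects failing while uncovered: (1/29) x the sum over g = 1 to 13 of [1 - exp(-h1 x g/7)]. This is 5.7% at p = 0.65 (h1 = 0.1397) and 8.8% at p = 0.50 (h1 = 0.2248).

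**5. Bias.** Let m be the fraction of those failures never recorded by any route. The documents do not give m; 10-25% is assumed.

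| True success rate | Failing while uncovered | Overstatement, m = 10% | Overstatement, m = 25% |
|---|---|---|---|
| 65% | 5.7% | 0.6 points | 1.4 points |
| 50% | 8.8% | 0.9 points | 2.2 points |

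**6. Effect on false success.** The Main-study effectiveness rule was simulated at a true 50% rate under step 4: 185 subjects, expected enrolment, 12% yearly dropout, interim threshold 0.9975 and final threshold 0.9775. Results are ranges over the stated Gamma(1,1) hazard prior and a near-flat one.
- No loss: about 0.6-0.8%. Appendix D Table 4 gives 0.7-1.1% at a 1% adverse-event rate.
- m = 10%: about 1.1-1.4%.
- m = 25%: about 2.5-2.9%, which is at or just above the 2.5% limit.

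**7. End of weekly transmission.** On the 30-day month of Protocol 13.7, month 5 ends on Day 150 and the 6-month visit is nominally Day 180. The difference is 30 / 7, or about four weekly transmissions. The 6-month window is Days 150-210, so the difference is nil for a visit on Day 150 and larger for a late visit.

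**The case against.** The best defence is that the text sets an outer limit, not a plan to issue late. The visit is centred on Day 90, 15 of its 29 days fall before Day 91, earlier issue is allowed, and section 13.10 states the intent of weekly transmission during Days 91-365. This stands as a limit on size. It does not close the gap, because a site that issues on Day 104 is compliant.

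It is also fair that much of the early hazard may not need a TTM. The pattern is taken from an earlier catheter and is not broken down by type of failure. The endpoint here also counts acute procedural failure, repeat-ablation failure and antiarrhythmic drugs carried past Day 90 (Protocol 8.2.2, Table 12.1A), several of which are settled at or near Day 91. A 12-lead ECG is due at the 3-month visit, unscheduled visits are possible, and weekly transmission follows. These routes stand, with the reservation that the ECG is a single recording and that the visit may be held by telehealth or phone.

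Three stronger readings are tempting, and the documents do not support them.
- *About 70% of failures would be missed.* That figure is the share of modelled failures in the window, whatever their type and however they are detected.
- *Half the subjects lose the full two weeks.* This would give 0.5 x 24.4% = 12.2% of subjects failing uncovered, about twice the 5.7% in step 4. Only a visit on or near Day 104 comes close to a two-week gap; a Day 97 visit loses six days.
- *Type I error is broken.* If every device were issued on Day 104, losing 10% of the exposed failures would raise an apparent rate of 50% to 53.4% and false success to about 5-6%. Nothing in the documents suggests that all subjects would be seen on the last permitted day.

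**Conclusion.** The gap is real and favours the device. As written, the plan allows up to 13 days of the evaluation period without a TTM, in the stretch where its own model has the highest hazard. The likely size is modest: about 0.6-1.4 points of overstated success at a true 65% rate and 0.9-2.2 points at 50%. These figures rest on three assumptions that the documents cannot confirm: uniform visit dates, issue at the visit, and 10-25% of uncovered failures never recorded. Applying that loss to every modelled failure, including those that need no TTM, tends to overstate the effect; visits clustered late in the window would understate it. False success stays below 2.5% at the lower loss and reaches about that limit at the upper one. The plan should be changed because the gap is easily avoided, not because the result would be unsafe without the change. The two end dates for weekly transmission are a genuine but secondary inconsistency.

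**What to change.** 1. In the synopsis and Protocol 13.10, require TTM issue and the test transmission by Day 90, whenever the 3-month visit takes place, with the first scheduled transmission in the week of Day 91. Align the TTM row of Table 13.8A.
2. State one end point for weekly transmission in both places: either the 6-month visit or the end of month 5.
3. For subjects whose devices are already out, report the issue day relative to Day 91, so that the actual gap replaces the assumed one.

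Sample size and decision thresholds do not change. The cost is a wording amendment, earlier shipment, and slightly longer device time per subject. The documents give no device budget, so that cost cannot be stated in money.

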## **13.11** Repeat AF Ablation Procedures

Repeat AF ablations(s) may be performed at the discretion of the physician. The followup schedule (Medication Adjustment and Therapy Consolidation periods and exam intervals) will continue based on the initial AF ablation procedure performed, regardless of repeat ablations.

The following assessments should be performed before each procedure:

- Imaging for detection of LA thrombus performed within 48 hours prior to the procedure (refer to Section 13.2 for details).
- Pregnancy Test Pre-menopausal women only, performed within 48 hours prior to the procedure.

Note: All subjects who undergo a repeat ablation procedure during blanking period with the QDOT MICROTM catheter will undergo follow-up for Day 7 and 1 month after the ablation procedure.

## **13.12** Core Laboratory

A core laboratory will be used to review the ECGs, TTMs and Holter Monitors for the objective evaluation of recurrence of atrial tachyarrhythmias. Evaluations will be reviewed by a physician. AF episodes will be evaluated per the definition included in this protocol. A core lab will also be used to review the CT/MRA images.

## 14.0 ASSESSMENT OF SAFETY

#### 14.1 Adverse Event Recording

An Adverse Event is any untoward medical occurrence, unintended disease or injury, or untoward clinical signs (including abnormal laboratory findings) occurring during a clinical study, whether or not related to the study device or ablation procedure.

For the purposes of this protocol, adverse events will be reported and recorded (via eCRF) if any of the following apply:

- Event is vascular, cardiovascular, or neurologic in nature
- The event is a serious adverse event
- Causality is related to:
  - Investigational device
  - Ablation procedure
  - Unknown in nature

The following clinical events will not be considered an adverse event for this clinical study:

- Any medical condition that is present at the of screening. Such conditions should be added to the medical history, if not previously reported. However, if the study subject's condition deteriorates at any time during the study, it should be recorded as an AE.
- A trace / trivial pericardial effusion that is asymptomatic, requires no medical intervention, and does not extend hospitalization will not be considered an adverse event
- Recurrence of pre-existing AF/AT/AFL
- AF/AFL/AT recurrence requiring pharmacological or direct current cardioversion at any time throughout the duration of the study. However, new onset of left atrial flutter occurring post-ablation is an AE.

• Re-ablation for AF or pre-existing AFL/AT itself is not an AE, however any complication associated with the repeat ablation procedures is considered an AE and shall be reported within the applicable timelines.

Subjects should be encouraged to report AEs spontaneously or in response to general, non-directed questioning (e.g., "How was your health been since last visit?"). Anytime during the study, the subject may volunteer information that resembles an AE.

The investigator is responsible for ensuring that all reportable AEs, observed by the investigator/study staff or reported by the subject, that occur from the time that the subject has signed the informed consent through the end of the study are properly assessed, recorded, and reported as defined and described in the AEs, Adverse Device Effects and Device Deficiencies section of this protocol and whenever the physician becomes aware of an event. Investigators will determine, at each encounter, whether any adverse events (AE) have occurred, and judge their seriousness and relationship to the study device and procedure. Each investigator shall provide source documentation as requested by the Sponsor to facilitate reporting and adjudication of these events.

All adverse events meeting the above definitions, regardless of classification, seriousness, intensity, outcome, or causality, must be recorded in the electronic CRF(s) in a timely manner throughout the study. Onset date of the event, its treatment, current status (resolved, stabilized, or ongoing), and assessment of its seriousness and relationship to the device should be provided when available. All AEs will be monitored until they are resolved or stabilized (no further changes anticipated).

## 14.2 Classification

Any of the following events, and any death or hospitalization while on study, is to be reported to the sponsor immediately. The Sponsor may request additional information after the initial notification.

## 14.2.1 Primary Adverse Event

A Primary AE is one of the following events occurring within seven (7) days following an AF ablation procedure with the QDOT MICROTM catheter when used with the nMARQTM RF generator, except atrio-esophageal fistula and PV stenosis, which may also be considered as primary adverse events if occurring greater than seven (7) days and up to 90 days post the ablation procedure:[55, 56]

